7.2.2 Main Analytical Approach

The following approach (details are provided further down) is to be applied:

1. For subjects who **received at least 15% increase** in average pill count of rescue analgesic medications (**categorized as Non-Responder** per Table 7.1) OR upgraded from Tier 1 to Tier 2 or Tier 1+Tier 2 compared to Baseline measurement cycle, the change from baseline (CFB) in means of DYS measured by NRS at Week 6 measurement and/or Week 12 measurement will be handled per the following two scenarios:
 - a. If **CFB ≥ 0** , the CFB will be kept as it is.
 - b. If **CFB < 0** , the CFB will be **set to Zero**.
2. **Any missing** mean changes in DYS measured by NRS at Week 6 and/or Week 12 are **multiple imputed using a MAR approach**.
3. Any (observed or imputed) mean changes in DYS measured by NRS at Week 6 measurement and/or Week 12 measurement **after premature withdrawal** from study treatment (one of ICEs) is **set to missing and then multiple imputed using a missing-not-at-random (MNAR) approach**.

Multiple Imputation (MI) Approach

In the MI approach, the mean changes in DYS measured by NRS are multiple imputed: plausible values obtained from a prediction model applying first a MAR approach, followed by a specific MNAR approach applied for hypothetical strategy for handling the specific ICE.

As a monotone missing pattern cannot be expected, the fully conditional specification (FCS) method is used for dealing with arbitrary non-monotone missing data patterns. FCS is based on an iterative algorithm; at each iteration and for each variable of the prediction model, there is a prediction step and an imputation step. When missing values for the last variable in the sequence have been imputed, the algorithm cycles again through each variable, repeating the chain of regression estimation and imputation draw steps.

The full MI approach comprises of 4 steps:

- **Prediction Step:** current (iteration) values of the observed and imputed values are used to derive the predictive distribution for missing values under MAR, under MNAR mechanism also a function of the selected subset of observations (premature withdrawal from study treatment).
- **Imputation Step:** updated imputations are generated by draws from the predictive distribution defined by the updated regression model (prediction and imputation are done simultaneously by SAS Proc MI).
- **Analysis Step:** analysis based on analysis of covariance models (ANCOVA) model (obtaining a point estimate and its standard error for mean change difference in DYS measured by NRS at Week 12) is conducted for each of the multiple imputed datasets by using SAS Proc GLM.
- **Combining Step:** SAS Proc MIANALYZE is used for combining the point estimates and standard errors obtained in the analysis step from the multiple imputed datasets, in order to provide a single point estimate and confidence interval.

The seed used by in the predication and imputation steps is 264156.

Prediction and Imputation Steps Assuming MAR:

The prediction step assuming MAR attempts to predict the mean changes in DYS measured by NRS based on observed data.

The prediction model will be a regression model with the following variables: treatment group, randomization strata of region , baseline DYS measured by NRS, and mean changes in DYS measured by NRS at Week 6 and Week 12. The algorithm cycles are repeated 200 times (“burn-in” iterations) and finally there are 25 draws from the predictive distribution for missing values. SAS Proc MI is used for this process.

The following SAS code for MI based on FCS method will be used:

```
PROC MI data=data_in out=data_out1 n impute=25 Seed=264156;
CLASS trt01p region;
FCS NBITER=200 REG(chg_dys_w6=trt01p region baseline_dys);
FCS NBITER=200 REG(chg_dys_w12=trt01p region baseline_dys chg_dys_w6);
VAR trt01p region baseline_dys chg_dys_w6 chg_dys_w12;
RUN;
```

Prediction and Imputation Steps Assuming MNAR for Premature Treatment Discontinuation:

For the ICE with hypothetical strategy, subsequent to the MAR imputation (described above), mean changes in DYS measured by NRS after such ICE are set to missing and a further multiple imputation is applied based on a specific MNAR mechanism: the now missing mean changes in DYS measured by NRS will be imputed by predictions using only data from subjects who did not experience the ICE with hypothetical strategy. The MNAR prediction model is indicated below.

The following SAS code for MI with MNAR assumption will be used:

```
PROC MI data=data_out1 out=data_out2 n impute=25 Seed=264156;
BY _imputation_;
CLASS trt01p region;
FCS NBITER=200 REG(chg_dys_w6=trt01p region baseline_dys);
MNAR MODEL(chg_dys_w6/MODELOBS=(ICE2='No'));
FCS NBITER=200 REG(chg_dys_w12=trt01p region baseline_dys chg_dys_w6);
```

```
MNAR MODEL(chg_dys_w12/MODELOBS=(ICE2='No'));
VAR trt01p region baseline_dys chg_dys_w6 chg_dys_w12;
RUN;
```

Analysis Step

For each of the $25 \times 25 = 625$ resulting datasets, the **ANCOVA model** with treatment, region as the fixed effects and baseline DYS measured by NRS as covariate will be used to obtain point estimate and its standard error for mean treatment different in DYS measured by NRS at Week 12.

The following SAS code for ANCOVA will be used:

```
PROC GLM data=indata;
  BY _imputation_MAR _imputation_MNAR;
  CLASS trt01p region;
  MODEL cfb = trt01p region baseline;
  LSMEANS trt01p /cl;
run;
```

Combining Step

As a final step, SAS Proc MIANALYZE is used for combining the $m=625$ point estimates and associated standard errors (from the analysis step above) are combined in order to provide a single point estimate and confidence interval for final statistical inference on the null hypotheses.

A descriptive summary of the average DYS measured by NRS as well as change from baseline by treatment group and visit (measurements of Baseline, Week 6, Week 12, and Week 24) will be presented. The Week 24 measurement is defined in the section 7.3.1.

A by-subject listing of DYS measured by NRS will be provided.

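### SAP 7.2.2 chooses FCS for non-monotone gaps, but its code imputes Week 6 without Week 12, which can bias the primary effect slightly in either direction and slightly inflate its SE

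*SAP*

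**What the plan says.** All of this is in SAP 7.2.2 (Main Analytical Approach).

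- Reason for the method: "As a monotone missing pattern cannot be expected, the fully conditional specification (FCS) method is used".
- How it runs: after the last variable is filled, "the algorithm cycles again through each variable, repeating the chain of regression estimation and imputation draw steps".
- Variables in the prediction model: treatment, region, "baseline DYS measured by NRS, and mean changes in DYS measured by NRS at Week 6 and Week 12".
- Code, Week 6: "FCS NBITER=200 REG(chg_dys_w6=trt01p region baseline_dys".
- Code, Week 12: "FCS NBITER=200 REG(chg_dys_w12=trt01p region baseline_dys chg_dys_w6".

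The same two regressions appear in both PROC MI calls. The first call is the MAR step. In the second (MNAR) step, values after premature withdrawal from treatment are set to missing and then "imputed by predictions using only data from subjects who did not experience the ICE with hypothetical strategy". Each step makes 25 imputations.

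**The concern.** The rationale, the cycling description and the code do not describe the same procedure. In the code, Week 12 borrows from Week 6 but Week 6 never borrows from Week 12. That is a one-way sequence: the 200 burn-in cycles carry nothing back to Week 6. The pattern that separates a non-monotone from a monotone problem here, Week 6 missing with Week 12 present, is the one the code does not use properly.

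The pattern can occur. SAP 7.2.1 requires a captured cycle with at least 2 days of menstruation for each measurement, so a subject can lack a usable Week 6 cycle and still have a Week 12 one. The approach is reused for the sensitivity analysis (7.2.3), the PPS and FAS repeats (7.2.4) and the secondary pain endpoints (7.3). For dyspareunia on the Daily Impact scale, not-applicable answers count as missing (7.3.4), so intermittent gaps are likelier there.

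At stake are a small loss of accuracy and precision in the primary estimate, and its reproducibility: a programmer working from the rationale and one copying the code could obtain different answers.

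**Working it through.** **1. The plan's own figures.** The documents state no bias or SE effect for the imputation code, so the check starts from their design figures: SD 2.0, two-sided 0.05 and 34 evaluable per arm (SAP 1.4, 7.1), and a between-group difference of 1.4 (Protocol 9.2).

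- Within group, paired t, n = 34, difference 1: noncentrality 1/(2/√34) = 2.915, power 80.8%. The SAP's 80% is reproduced.
- Between groups, 34 per arm: SE = 2√(2/34) = 0.485, noncentrality 1.4/0.485 = 2.886, power 81.2% (normal approximation 82.3%). The Protocol's 80% is reproduced.

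**2. Mechanism.** Suppose a share p of subjects with Week 12 observed have Week 6 imputed from treatment, region and baseline only. Their imputed Week 6 has no residual covariance with Week 12, so the fitted slope falls from β to about (1 − p)β.

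Treatment is in both regressions, so a flatter slope does not by itself shrink the treatment effect. It under-corrects an arm's mean by about m × pβ × d. Here m is the share of that arm missing Week 12, and d is how much worse those subjects' Week 6 scores are than those of the rest of the arm.

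- d similar in all arms: the errors cancel.
- d > 0 in placebo only: placebo looks too good, and the effect is attenuated.
- d > 0 in an active arm only: that arm looks too good, and the effect is exaggerated.
- p = 0: no error.

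A subject with Week 12 observed and no withdrawal keeps her observed value (subject to the rescue rule), so the error enters only through imputed Week 12 values.

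**3. Simulation of the MAR step.** 1000 trials per scenario; 4 arms of 38; SD 2.0; true 240 mg minus placebo effect −1.4; 25 imputations; ANCOVA; Rubin's rules. The code as written was compared with the same code plus `chg_dys_w12` in the Week 6 model.

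Assumptions not in the documents: Week 6/Week 12 correlation 0.6 and 0.8; Week 6 missing in 0, 5, 10 or 20%; Week 12 missing in about 9-12%.

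Mean shift, code as written minus corrected (positive = toward the null), with Week 6 missing in 5-20%:

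| Week 12 loss | Shift (points) | SE ratio |
|---|---|---|
| Completely at random | within 0.001 | 1.003-1.014 |
| Depends on Week 6, alike in all arms | within 0.003 | 1.001-1.005 |
| Poor Week 6 responders, placebo only | +0.016 to +0.066 | 1.002-1.016 |
| Poor Week 6 responders, 240 mg only | −0.013 to −0.065 | 1.003-1.014 |

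The largest shifts are 0.0663/1.4 = 4.7% and 0.0649/1.4 = 4.6% of the effect. The corrected code gave −1.421 to −1.430 throughout, against −1.426 with complete data. With no Week 6 missing, the two versions agreed within 0.003 and the SE ratio was 1.000.

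**4. Wider rates.** A smaller run (250 trials per scenario, 38 per arm, assumed correlation 0.7):

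| Week 6 / Week 12 missing | SE increase | Shift: at random / placebo loss / 240 mg loss |
|---|---|---|
| 10% / 10% | 0.5-0.6% | about 0 / +0.015 / −0.013 |
| 20% / 15% | 1.5-1.7% | +0.002 / +0.036 / −0.040 |
| 40% / 20% | 2.3-2.4% | −0.009 / +0.065 / −0.068 |

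**5. Power.** By the normal approximation, power is Φ(2.886/k − 1.960) for SE ratio k. It is 82.3% at k = 1, 81.1% at k = 1.016 and 80.5% at k = 1.024: a loss of about 1 to 2 percentage points at the upper end.

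**6. The second PROC MI call.** The first call has filled every gap, and only post-withdrawal values are then blanked. Withdrawal before the Week 6 measurement removes both values; later withdrawal removes Week 12 only. Week 6 is therefore never missing with Week 12 present, and the pattern is monotone by construction. The order in the code is adequate there, although the regression still uses the Week 6 values filled in by the first call. This second step was not simulated.

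**The case against.** **The effect may be negligible.** The only attrition figure in the documents is up to 10% premature discontinuation (SAP 1.4), which produces mainly monotone gaps. The Week 6 measurement takes the closest menstruation before or after the Week 7 visit and averages whatever diary days exist, which limits isolated gaps. With Week 6 missing in 2-10%, Week 12 loss of about 9% depending on Week 6, and an assumed correlation of 0.7, the shift was −0.001 to +0.007 points and the SE increase 0.1-0.3%. This stands, and it is why the point is a small improvement and not a threat to the trial.

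**The text does not call the two visits mutual predictors.** It gives one list of variables, and that list matches the VAR statement. This also stands. The conflict is between the code and the reason given for FCS together with the description of cycling, not with an explicit instruction to put Week 12 in the Week 6 model.

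**A reader might infer that the code attenuates the Week 12 effect.** Neither the documents nor the algebra supports that as a general result. The sign depends on which arm loses poor Week 6 responders, and the shift is about nil when loss is alike across arms.

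**A reader might also infer that both PROC MI calls are faulty.** The second is not, since its missing pattern is monotone.

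**Conclusion.** The mismatch is real. The code is a one-way sequence that disregards the observed Week 12 score of a subject whose Week 6 is missing, whereas the SAP chose FCS because such patterns were expected. The primary effect may be biased slightly in either direction: about 0 under non-differential loss, and up to about 0.07 points (about 5% of 1.4) toward or away from the null if poor Week 6 responders are lost mainly from one arm. Its SE is inflated by about 0.1-2.4%.

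These sizes hold for correlation 0.6-0.8, Week 6 missing in 5-40% and Week 12 missing in about 9-20%, all assumed, and for the MAR step alone. They vanish if no subject has Week 6 missing with Week 12 observed. It would be too strong to say that the code defeats the planned analysis.

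**What to change.** In the first (MAR) PROC MI call, use `REG(chg_dys_w6 = trt01p region baseline_dys chg_dys_w12)`. The same term may be added to the second call so that the two blocks match, but it is not needed there. Carry the change into the analyses that reuse this code.

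If a sequential model was intended, say so in 7.2.2, justify it, and drop the non-monotone rationale and the cycling description.

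The cost is one term in one line of code, with no effect on design, data collection or clinical conduct. How the 25 × 25 = 625 nested data sets are pooled is a separate question, to be raised on its own.

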7.1 Discontinuation of IMP

It may be necessary for a subject to permanently discontinue (definitive discontinuation) the IMP. If the IMP is definitively discontinued, the subject will remain in the study until Visit 10 to be evaluated for safety and efficacy of the IMP. Please refer to Section 10.4 and 8.4.5 for details on contraceptive guidance and collection of pregnancy information.

The Investigator or Medical Monitor (and, if needed, with DMC review) may temporarily hold or stop the dosing of IMP to a subject at any time during the study. For subjects that discontinue IMP for reasons related to safety, unblinding of the treatment assigned to the subject may be carried out if deemed necessary by the Sponsor to assess any potential safety signal or by the Investigator to provide adequate medical care to the subject. All details of reasons, therapies that may have been subsequently started should be well documented and reviewed.

Examples of conditions or symptoms that may warrant holding or stopping IMP at the Investigator's and/or Medical Monitor's discretion include:

- Occurrence of a severe or serious AE assessed as related to IMP
- Repeating premature ventricular contractions (PVC) confirmed by additional ECG examination at least 30 minutes apart, or QTcF interval >500 ms, or increase in QTcF interval >60 ms compared to baseline in absence of possible causes other than the IMP
- Significant decrease of neutrophils count < 1500 mm³ confirmed by repeat measurement

Version 6.0 45 of 138 April 11, 2024

- Pregnancy
- Intolerance of the IMP authorized under this protocol
- If in the Investigator's opinion, continuation with the administration of the IMP would be detrimental to the subject's well-being

Investigator must notify the Sponsor within one calendar day of being aware of an event that may warrant holding or stopping the IMP. If the IMP is held due to safety concerns, approval by the Medical Monitor is required prior to resumption of IMP. If the subject meets the holding or stopping conditions again after resumption (re-challenge), the IMP will be permanently discontinued.

Unless informed consent is withdrawn, subjects who permanently discontinue IMP during the treatment period should attend all subsequent visits up to Visit 10 and complete all procedures (except IMP administration related) as outlined in the SoA.

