9.2 Sample Size Determination

152 eligible subjects will be randomly assigned to HMI-115 or placebo group and 136 evaluable subjects for an estimated total of 34 evaluable subjects per treatment group A sample size of 34 evaluable subjects per treatment group is planned. With an assumption that up to 10% of subjects may prematurely discontinue the study without providing data for efficacy evaluations,

Version 6.0 60 of 138 April 11, 2024

enrollment of approximately 38 subjects per treatment group is planned. With 38 subjects per group, there is an 80% power to detect a 1-point difference in the CFB to Week 12 in DYS NRS within a treatment group. This is based on the assumption of a standard deviation (SD) of 2.0 and a paired t-test at the 0.05 alpha level. This sample size is also expected to provide adequate precision in the point estimate and 95% confidence interval (CI) of the CFB for each treatment group.

Because this is a proof-of-concept study, the sample size is planned to provide adequate data to evaluate the efficacy and safety of HMI-115 in the dose range studied. It is not based on power calculation to demonstrate statistically significant difference versus placebo. However, in the context of comparing an HMI-115 treatment group versus placebo (ie, between-group comparison), this sample size will provide 80% power to detect a treatment difference of 1.4 point in the CFB in DYS NRS based on the assumption of SD of 2.0 and a 2-sample t-test at 0.05 significance level.

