7. EFFICACY

7.1 Analysis and Data Conventions

The null hypothesis is that there is no difference between each HMI-115 treatment group and placebo in mean change of DYS measured by NRS from Baseline to Week 12. The alternative hypothesis will be that there is a difference.

All efficacy analyses will be conducted using the PAS. PPS and FAS will be the supplements for partial efficacy analyses. Each comparison will be carried out at the two-sided 5% level of statistical significance unless otherwise specified.

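### The primary analysis pools 625 nested imputations with a rule that ignores the nesting, and fits its first imputation model before off-treatment scores are removed; the effect on the primary result is small and cheap to correct

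*SAP*

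**What the plan says.** SAP 7.2.2 works in stages. After an adjustment for increased rescue use, missing Week 6 and Week 12 changes in the dysmenorrhea (DYS) score are imputed 25 times under MAR. Step 3 then takes "Any (observed or imputed) mean changes in DYS measured by NRS at Week 6 measurement and/or Week 12 measurement" that fall after withdrawal from treatment, sets them to missing and re-imputes them. The detailed text confirms the order: "subsequent to the MAR imputation (described above), mean changes in DYS measured by NRS after such ICE are set to missing". The second PROC MI call runs separately within each first-stage dataset, again with 25 draws, and is fitted only to women without the withdrawal event.

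ANCOVA is run on each of the 625 datasets. The 625 "point estimates and associated standard errors (from the analysis step above) are combined in order to provide a single point estimate and confidence interval", using PROC MIANALYZE. Code is printed for both PROC MI calls and for PROC GLM, but not for MIANALYZE. Neither a nested combining rule nor a complete-data df is mentioned.

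SAP 7.2.1 gives treatment withdrawal a hypothetical strategy. Under Protocol 7.1, women who permanently stop treatment without withdrawing consent "should attend all subsequent visits up to Visit 10 and complete all procedures". The secondary pain endpoints in SAP 7.3 follow the same steps. On testing, SAP 7.1 says: "Each comparison will be carried out at the two-sided 5% level of statistical significance unless otherwise specified".

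**The concern.** Three features of the procedure bear on the primary interval and estimate.

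- **Nesting.** The 25 second-stage datasets that share a first-stage draw are correlated. The standard combining rule treats all 625 as independent and so understates the between-imputation variance.
- **Degrees of freedom.** If MIANALYZE is run without a complete-data df, the critical value is effectively the normal one, although the ANCOVA has only N − 7 residual df.
- **Order of deletion.** Scores recorded after a woman stops treatment are present when the MAR model is fitted. They can shape imputed values for women in the same arm who are still on treatment. The second stage excludes the withdrawn women from its fitting set, but it is then fitted to those on-treatment imputations. If the effect is lost off treatment, the estimate moves towards placebo, contrary to the hypothetical strategy.

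At stake are the width of the primary confidence interval, the p-value that goes with it, and the agreement between estimand and estimator. The secondary endpoints inherit the same procedure.

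**Working it through.** **Plan figures reproduced.** Protocol 9.2 says "this sample size will provide 80% power to detect a treatment difference of 1.4 point in the CFB in DYS NRS". Its inputs are a common SD of 2.0, a two-group t-test at the 5% level, and an "estimated total of 34 evaluable subjects per treatment group". The non-centrality is 1.4 / (2.0 × √(2/34)) = 2.89, and the exact two-sample t-test gives 81.2% at 34 per arm (85.3% at 38). The 80% is reproduced. The dataset count is 25 × 25 = 625.

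**Nesting.** Take M = 25 nests of N_w = 25 draws, between-nest variance sb², within-nest variance sw² and average complete-data variance U.

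- Standard rule: T = U + (1 + 1/625)B. The weight on sb² is (626/625) × (24 × 25)/624 = 0.963.
- Nested rule: T = U + (1/N_w)(1 + 1/M)MSb + (1 − 1/N_w)MSw. The weight on sb² is 1 + 1/25 = 1.04.
- The weight on sw² is 1.0016 under both rules, so the shortfall is 0.077 × sb².
- With the simulated base-case values sb²/U = 0.0448 and sw²/U = 0.1010, the standard rule gives T/U = 1 + 0.0431 + 0.1012 = 1.1443 and the nested rule gives 1 + 0.0466 + 0.1012 = 1.1478. The half-width ratio is √(1.1478/1.1443) = 1.0015, or about 0.2%.

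**Degrees of freedom.** Without a complete-data df, df = 624(1 + 1/r)² with r = 0.1443, which is about 39,000; the simulated median was 41,684. The ANCOVA has 1 intercept, 3 treatment, 2 region and 1 baseline parameters, so its residual df are N − 7. The size of the primary analysis set (the surgically diagnosed women) is not given, so a range of N is shown against 1.960:

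| N | df | t critical value | Wider by |
|---|---|---|---|
| 152 | 145 | 1.976 | 0.8% |
| 136 | 129 | 1.979 | 0.9% |
| 100 | 93 | 1.986 | 1.3% |

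The small-sample pooled df are lower than N − 7 (median 124 at N = 152), which makes the widening 1.0% there.

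**Simulation of the whole procedure.** 2,800 trials per scenario. Assumptions not in the documents: the withdrawal and missingness rates shown, the share of withdrawn women who have off-treatment scores, full loss of effect off treatment, Week 6–Week 12 correlation 0.6, residual SD 2.0, and N. The effect is 1.4 points except in E, where it is zero. "Other missing" means missing scores that do not follow withdrawal.

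| | N | Withdrawal | With off-treatment scores | Other missing | Width ratio: df only | Nested rule only | Both | Coverage as written | Coverage with both | Dilution (points) |
|---|---|---|---|---|---|---|---|---|---|---|
| A | 152 | 10% | 50% | 5% | 1.010 | 1.002 | 1.011 | 94.0% | 94.3% | 0.003 |
| B | 136 | 10% | 50% | 0% | 1.011 | 1.000 | 1.011 | 94.7% | 94.9% | 0.000 |
| C | 100 | 15% | 100% | 10% | 1.017 | 1.004 | 1.021 | 95.2% | 95.5% | 0.019 |
| D | 100 | 20% | 100% | 20% | 1.021 | 1.009 | 1.030 | 95.9% | 96.3% | 0.055 |
| E | 152 | 10% | 50% | 5% | 1.010 | 1.002 | 1.011 | 95.1% | 95.3% | 0.000 |

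The Monte Carlo SE of coverage is √(0.95 × 0.05/2800) = 0.4 points. Width ratios are relative to pooling as written without a complete-data df; in A the half-width goes from 0.971 to 0.982. Dilution is the difference between the estimate as written and the estimate with off-treatment scores removed before the MAR step. The largest, 0.055, is 3.9% of 1.4.

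**The case against.** **The df point is silence, not a choice.** No MIANALYZE code is printed, so a complete-data df might be set when the analysis is programmed. That stands. It matters because df accounts for most of the width effect. The nesting and the order of deletion, however, are stated outright.

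**A reader might infer that the primary interval and p-value are anti-conservative.** The results do not support that as a flat statement. The interval is narrower than the reference formula gives, but coverage as written is 94.0–95.9%. The 94.0% in A is 2.4 Monte Carlo SEs below nominal, yet the same design under the null gives 95.1%. In C and D the standard error as written already exceeds the empirical SD (0.650 against 0.628, and 0.712 against 0.665).

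**The dilution needs several conditions.** Some women still on treatment must have missing scores, and no document gives a rate. SAP 7.2.1 averages whatever diary days exist, so partial diary loss does not by itself remove a score. The effect must fade off treatment, but Protocol 4.4 sets the Week 25 visit to cover five half-lives: Day 71 to Day 169 is 98 days, or about 20 days per half-life. Attendance after stopping is expected rather than assured, and the planned 10% dropout is of women who provide no efficacy data. All this stands as a limit on size. On-treatment missingness is nevertheless plausible, because a Week 12 score needs a complete cycle with at least two days of menstruation.

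**A reader might also expect serious harm in the regional subgroups.** The documents give no subgroup sizes, and SAP 7.1.6 plans no formal analysis within subgroups, so no such claim is made.

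**Conclusion.** The point holds in a limited form. Two stated rules are not right: pooling 625 nested datasets by a rule for independent ones, and fitting the MAR model before the scores that the estimand excludes have been removed. A third item, the complete-data df, is unspecified.

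Together, and if no complete-data df is set, they make the primary interval about 1% too narrow at the planned size, of which about 0.2% is nesting, and about 3% too narrow in the adverse case. The estimate is diluted by 0.00–0.06 of 1.4 points. If every missing score follows withdrawal, nesting and dilution both vanish and only the df question remains. The sizes depend on the assumed missingness, the assumed full loss of effect off treatment and an assumed N of 100–152. Nothing here threatens the primary conclusion of a proof-of-concept trial. The reason to act is that the procedure conflicts with its own estimand and the correction is simple.

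**What to change.** In SAP 7.2.2, and so for the endpoints that follow it:

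1. Set all DYS changes after treatment withdrawal to missing before any imputation.
2. Use one imputation stage with at least 100 draws. Alternatively, keep two stages with NIMPUTE=1 in the second and at least 100 draws in the first, or keep the nested design and state nested combining rules.
3. Say whether the restriction of the fitting set to women without the withdrawal event is intended, and keep it if so. A plain single-stage run would also use on-treatment Week 6 scores from women who withdrew later.
4. Print the MIANALYZE code with EDF set to the ANCOVA residual df, N − 7 for the actual size of the analysis set.

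The cost is a few lines of code and intervals about 1–3% wider. A single stage of 100 draws also means fewer datasets than 625.

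Separately, Protocol 9.4.3 names jump-to-reference imputation for early discontinuation, while the SAP code predicts from women without the event using their own treatment arm. SAP section 10 does not list this as a change. The SAP cites protocol version 6.1 and the protocol available here is 6.0, so the current protocol text should be checked and the two documents reconciled.
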